4. DETERMINATION OF SAMPLE SIZE

The sample size in this trial was determined outside of statistical considerations. Twenty-six patients were considered adequate for point estimates with reasonable accuracy.

5. SAFETY, PHARMACODYNAMIC, AND PHARMACOKINETIC ASSESSMENTS

5.1 STUDY SCHEMATIC AND SCHEDULE OF ASSESSMENTS

The schedule of evaluations for Study C1973-202 is presented in [Table 2](#).

Table 2. Schedule of Events

Study Period→	Screening Period	Clinic Period				
		Screening Visit Day -28 to -3	Check-in Day -2	Day -1	Day 1	Day 2
Visit Days → Study Procedure ↓						
ICF Signed	X					
Demographics	X					
Medical History	X					
Inclusion/Exclusion Evaluation	X	X				
Physical Exam	X	X				
Hepatitis (HBsAg, HCV) & HIV Screen	X					
Drug & Alcohol Screen (a)	X	X				
Pregnancy Test (b)	X	X				
Weight (W) & Height (H) (c)	W, H		W			
12-lead electrocardiogram (d)	X	X		preAM: 0 ($\leq 30m$) pdAM: 4 ($\pm 15m$)		
Respiratory rate (R) & oral temperature (T)	X	X	X	T,R preAM: 0 ($\leq 30m$) T pdAM: 1, 4 h ($\pm 15m$)	X	X
Supine/standing BP & pulse (e) ³ indicates triplicate supine BPs supine only	AM PM	X ³	X	preD1: 0 ($\leq 30m$) ³ pdD1: 1, 4h ($\pm 5m$) preD1: 0 ($\leq 15m$) pdD1: 1, 4 h ($\pm 5m$)	pre: 0 ($\leq 30m$) pd: 1, 4h ($\pm 5m$) pre: 0 ($\leq 15m$) pd: 1, 4 h ($\pm 5m$)	pre: 0 ($\leq 15m$) pd: 1, 4h ($\pm 5m$) pre: 0 ($\leq 15m$) pd: 1, 4 h ($\pm 5m$)
Hemoglobin A1c		X	X		preAM: 0 ($\leq 15m$)	
Fasting plasma glucose & serum insulin (f)		X	X		preAM: 0 ($\leq 15m$)	
Clinical chemistry, coagulation, hematology, urinalysis (f)		X	X		serum creatinine only preAM: 0 ($\leq 15m$)	
Urine albumin & creatinine (g)	X		first void			
AE Evaluations	X	X	X	X	X	X
Prior & concomitant medications	X	X	X	X	X	X

Table 2. Schedule of Events

Study Period→	Screening Period	Clinic Period					Days 3-6
		Screening Visit Day -28 to -3	Check-in Day -2	Day -1	Day 1	Day 2	
Visit Days → Study Procedure ↓							
Ambulatory BP monitoring (i)				Start: preD1: 0 ($\leq 15m$)	Continue	End: pd 12h [= preAM: 0($\leq 15m$)]	
EndoPAT (j)				pre D13: 0 (end ≥ 30 m)			
Randomization					X		
Study drug administration (l)	AM				X	X	X
	PM				X	X	X
PK blood samples (m)	AM				pre: 0 ($\leq 15m$) pd: 1, 3, 6h ($\pm 5m$)	...pd 6h ($\pm 5m$) pre: 0 ($\leq 5m$)	
	PM				pre: 0 ($\leq 5m$) pd: 1, 3h ($\pm 5m$)...	pre: 0 ($\leq 5m$)	
Platelet function (n)					preAM: 0 ($\leq 15m$)		
Confined to clinic			X	X	X	X	X
Discharge from clinic							
Study completion							

AM = morning; BP = blood pressure; h = hour; H = height; HBsAg = hepatitis B surface antigen; HCV = hepatitis C virus; HIV = human immunodeficiency virus; ICF = informed consent form; m = minute; msec = millisecond; pd = postdose; pdD1 = corresponding to postdose Day 1; PM = evening; pre = predose; preD1 = corresponding to predose Day 1; R = respiratory rate; T = oral temperature; W = weight

- Urine drug screen for selected drugs of abuse and alcohol breathalyzer screen
- For female patients, a negative serum pregnancy test must be documented at the Screening Visit, at Check-in with results available before randomization, and at the Follow-up Visit. A urine pregnancy test must be documented at the End of Trial Visit.
- On in-clinic days, in the morning after voiding, before any water or food intake
- Patients must be supine for ≥ 5 minutes before the ECG recording (Note: If on initial ECG, QTcF is ≥ 450 msec for male patients or is ≥ 470 msec for female patients, the ECG will be repeated 2 more times, and the average of the 3 QTcF values will be used to determine the patient's eligibility).

- e. Triplicate supine to standing assessment (Screening Visit, predose on Day -1, and on Day 15) after the subject has been lying quietly for ≥ 5 m supine BP and pulse is the average of 3 measurements obtained at 2-m intervals, after final supine measurement subject assume sitting position for 1 m, and finally assume standing position for 2 m before standing measurements are taken Note: The change in blood pressure from supine to standing will be determined using the third supine blood pressure and pulse measurements in comparison to the standing blood pressure and pulse measurements. Single supine to standing measurement assessed after the patient has been lying quietly for ≥ 5 m before supine measurements are taken, then assume sitting position for 1 m, and finally assume standing position for 2 m before standing measurements are taken. Single supine measurements are assessed after the subject has been laying quietly for ≥ 5 m. Predose measurements should precede all oral and any antihypertensive concomitant medications. All measurements before blood draws where applicable. Note: Supine-only (without standing) pulse and BP may be taken at the 4-h post PM dose timepoints (approximately midnight) if, in the Investigator's clinical opinion, earlier postdose orthostatic (supine and standing) pulse and BPs for the given dosing and for previous dosings at the 4-hour postdose timepoint indicate it is safe to eliminate the standing (orthostatic) pulse and BP measurement.
- f. After ≥ 8 -h fast, after EndoPAT (when applicable) and BP/pulse measurements and before dosing, where applicable. Does not apply to urine collection.
- g. At the Screening and Follow-up Visit, single urine sample, which may not be first void; during Clinic Period, first-void urine sample
[REDACTED]
- i. ABPM assessments should be performed on the same arm of the subject throughout the study; non-dominant arm is preferred.
- j. If EndoPAT is available at the Study Center, for each patient, the Day -1 and Day 13 assessments should be at approximately the same time of day (± 15 m). Before all oral and any antihypertensive concomitant medications and study drug, BP/pulse measurements (for PD/Safety), and blood collections; after opportunity to void and then resting quietly in a temperature-controlled room for ≥ 15 m; occlusion/finger measurement right arm/hand. See [Protocol Section 3.7.4.2](#)
[REDACTED]
- l. 2 orally administered 8-tablet doses: an AM 8-tablet dose at \sim same time (± 15 m) every day after overnight fast of ≥ 8 hours on Days 1 to 12 and on Day 14. On Day 13, first dose may be administered in the morning between 7 and 10:30AM, after the EndoPAT assessment (if applicable). Breakfast should begin within 30 m after dosing. PM 8-tablet dose, 12 hours (± 30 minutes) after AM dose and ≥ 30 minutes after completing dinner. May take multiple tablets together. Permitted concomitant medications may be taken at the same time as study drug.
- m. ≈ 2 -mL blood sample in one K₂EDTA tube at each timepoint; each sample divided into 2 equal plasma aliquots
- n. CPRS assessment ≈ 1.8 -mL blood sample in one 3.2% citrate tube at each timepoint as well as ≈ 4.5 -mL blood sample in one 3.2% citrate tube at each timepoint; VerifyNow Aspirin Test and VerifyNow PRU Test ≈ 2 -mL blood sample in 3.2% citrate tube at each timepoint for each test.

Table 2. Schedule of Events (...Continued)

Study Period→	Clinic Period					Follow-up Period	
	Day 7	Days 8-13	Day 14	Discharge Day 15	Follow-up Visit Day 21 (± 2)	End of Trial Visit Day 42 (± 3)	
Visit Days → Study Procedure ↓							
ICF Signed							
Demographics							
Medical History							
Inclusion/Exclusion Evaluation							
Physical Exam					X		X
Hepatitis (HBsAg, HCV) & HIV Screen							
Drug & Alcohol Screen (a)						X	
Pregnancy Test (b)						X	X
Weight (W) & Height (H) (c)		Day 13 W			W	W	W
12-lead electrocardiogram (d)					X		
Respiratory rate (R) & oral temperature (T)	X	X	X	X	X	X	X
Supine/standing BP & pulse (e) ³ indicates triplicate supine BPs supine only	AM	pre: 0 ($\leq 15m$) pd: 1, 4h ($\pm 5m$)	Days 8 & 13 pre: 0 ($\leq 15m$) pd: 1, 4 ($\pm 5m$) Days 9-12 pre: 0 ($\leq 15m$)	pre: 0 ($\leq 15m$)	pd: 12h ($\pm 15m$) ³	☒	☒
	PM		Day 8 & 13 pre: 0 ($\leq 15m$)				
Hemoglobin A1c		Day 8	preAM: 0 ($\leq 15m$)	preAM: 0 ($\leq 15m$)	X		X
Fasting plasma glucose & serum insulin (f)		Day 8	preAM: 0 ($\leq 15m$)		X		
Clinical chemistry, coagulation, hematology, urinalysis; (f)					X		X
Urine albumin & creatinine (g)					first void		X
AE Evaluations	X	X	X	X	X	X	X
Prior & concomitant medications	X	X	X	X	X	X	X

Table 2. Schedule of Events (...Continued)

Study Period→		Clinic Period				Follow-up Period	
Visit Days →	Study Procedure ↓	Day 7	Days 8-13	Day 14	Discharge Day 15	Follow-up Visit Day 21 (± 2)	End of Trial Visit Day 42 (± 3)
Ambulatory BP monitoring		Start: pre: 0 (≤ 15 m)	End: Day 8 preAM: 0 (≤ 15 m)	Start: preAM: 0 (≤ 15 m)	End: pd: 12h (± 15 m)		
EndoPAT (j)			Day 13 preAM 0 (end ≥ 30 m)				
Randomization							
Study drug administration (l)	AM	X	X	X			
	PM	X	X	X			
PK blood samples (m)	AM	pre: 0 (≤ 5 m) pd: 1, 3, 6h (± 5 m)	Day 8 pre: 0 (≤ 5 m) pd: 1, 3, 6h (± 5 m)	pre: 0 (≤ 5 m) pd: 1,3,6h (± 5 m)	pd: 12h (± 15 m)	X	X
	PM	pre: 0 (≤ 5 m)	Day 8 pre: 0 (≤ 5 m)	pre: 0 (≤ 5 m)			
Platelet function (n)			Day 8 preAM: 0 (≤ 15 m)	preAM: 0 (≤ 15 m)			
Confined to clinic	X		X	X			
Discharge from clinic					X		
Study completion							X

5.2 SAFETY ASSESSMENTS

The following safety assessments are performed throughout the study, as indicated in the Schedule of Events.

- Adverse Events
- Physical Examination
- Height and Weight
- Vital Signs including oral temperature, respiratory rate, supine and standing pulse, and cuff BP measurements
- Laboratory Parameters
 - Serum Chemistry: albumin, alkaline phosphatase, alanine aminotransferase (ALT), aspartate aminotransferase (AST), bicarbonate, blood urea nitrogen (BUN), calcium, chloride, cholesterol, creatinine, gamma glutamyl transferase (GGT), glucose, HDL-c, lactate dehydrogenase (LDH), LDL-c (calculated), magnesium, phosphorus, potassium, sodium, total bilirubin, total protein, triglycerides, uric acid.
 - Hematology: hematocrit, hemoglobin, platelet count, RBC count, WBC count, WBC differential (basophils, eosinophils, lymphocytes, monocytes, and neutrophils [% and absolute]), RBC indices (mean corpuscular hemoglobin [MCH], mean corpuscular hemoglobin concentration [MCHC], and mean corpuscular volume [MCV], red blood cell distribution width [RDW]).
 - Coagulation: activated partial thromboplastin time (aPTT), Prothrombin time, INR.
 - Urinalysis: pH and specific gravity, bilirubin, glucose, ketones, leukocytes, nitrates, occult blood, protein, urobilinogen, microscopic, including bacteria, RBCs, WBCs per high power field (HPF) only if dipstick is abnormal.
 - Additional tests: Hemoglobin A1c, fasting plasma glucose, fasting plasma insulin, urine albumin, urine creatinine
- 12-lead Electrocardiogram (ECG)
- Urine Creatinine Ratio (UACR)
- Estimated Glomerular Filtration Rate (eGFR)

5.3 PHARMACODYNAMIC ASSESSMENTS

The following hemodynamic, endothelial function, metabolic function, and platelet function assessments will be performed throughout the study, as outlined in the Schedule of Assessments.

Ambulatory Blood Pressure (BP) Monitoring:

Patients will undergo 24-48 hour ambulatory BP monitoring on Days -1, 7 and 14. The 48 hour monitoring will begin on Day -1 at the time that corresponds to “just before dosing” on Day 1 and will end on Day 2, 24 hours after dosing on Day 1. The 24-hour assessments will be performed on Day 7 and Day 14. The 30-minute, 4-hour, 24-hour, daytime, and nighttime averages of systolic BP, mean arterial pressure (MAP), and diastolic BP, and pulse measurements will be calculated.

Supine Pulse and BP Assessments:

Supine and standing BP and pulse measurements will be obtained after both the AM and PM doses, as outlined in [Table 2 - Schedule of Events](#).

Endothelial Function Assessments:

Endothelial function in the finger will be measured using the noninvasive EndoPAT™ (Itamar Medical; Caesarea, Israel) device on Day -1 and 13 at approximately the same time of day. All measurements will precede all antihypertensive concomitant medications and will be performed in a quiet, dimly lit, temperature controlled room after the patient has been resting quietly for 15 minutes. The right arm will be used for occlusion and finger measurements. Endothelial function will be assessed using the Reactive Hyperemia Index (RHI) parameter. Exploratory vascular physiology parameters such as Augmentation Index (AI) and AI adjusted to a heart rate of 75 beats per minute (AI-75) will also be assessed by the EndoPAT device.

Metabolic Function Assessments:

Homeostatic Model Assessment to Quantify Insulin Resistance (HOMA-IR)

Blood samples for determination of fasting blood glucose and insulin levels collected at Screening, Days -2, 1, 8 and 15 will be used to estimate insulin resistance using the Homeostatic Model.

Hemoglobin A1C, cholesterol, HDL, LDL, and triglyceride levels will be determined from blood samples collected as part of the safety laboratory assessments as specified in [Section 5.2](#).

Platelet Function Assessments:

Blood samples for platelet function assessment using Verify Now® instrument and evaluation of platelet function markers will be collected prior to dosing on Day 1, 8, and 14. Additional platelet function testing may also be performed.

[REDACTED]

[REDACTED]

[REDACTED]

[REDACTED]

[REDACTED]

[REDACTED]

5.4 PHARMACOKINETIC ASSESSMENTS

Blood samples for PK assessments will be collected as outlined in the Schedule of Events, and PK parameters may be calculated if systemic levels of IW-1973 are detectable, and data support the calculations.

6. STATISTICAL METHODS

6.1 GENERAL METHODOLOGY

Descriptive statistics (number of patients, mean, standard deviation, median, 25th and 75th percentiles, minimum and maximum) will be calculated for continuous variables. For summaries of continuous PK parameters, the geometric mean and the coefficient of variation (CV) will also be presented. For categorical variables, frequencies and percentages for each category will be presented. Percentages will be based on the total number of patients with non-missing values. If there are missing values, the number missing will be presented, but without a percentage. Data from screen failure subjects will be presented in subject data listings.

Inferential statistics, if calculated, will only be used for descriptive purposes.

All statistical analyses will be performed using SAS[®] Version 9.3 or later (1). Additional analyses using alternative software may be performed as part of the PK analysis.

Summary data for safety, PD and PK parameters will be presented by treatment group and IW-1973 overall, unless otherwise indicated:

- Placebo
- IW-1973 40 mg Total Daily Dose BID/QD
- IW-1973 40 mg Total Daily Dose QD/QD
- IW-1973 40 mg Total Daily Dose Overall

Summary data for PK parameters on Day 1 will be presented only for the 2 active treatment groups.

Definition of Baseline:

The following definitions of baseline will be used to calculate change from baseline parameters, unless specified otherwise:

- Study baseline is defined as the last non-missing assessment before first administration of study drug.

- For PD parameters obtained from ambulatory BP monitoring, time-matched baseline is calculated using the predose assessments on Day -1 that correspond to the respective postdose assessment timepoints.
- Trough baseline for supine BP and pulse assessments is defined as the Day 1 AM predose assessment.

6.2 ADJUSTMENTS FOR COVARIATES

Baseline will be included as a covariate in the analysis of covariance (ANCOVA) models used for the change from baseline PD parameters.

6.3 HANDLING OF DROPOUTS OR MISSING DATA

No imputation will be performed for missing PD observations. All safety and tolerability data will be summarized and analyzed when data values are available for a patient. Data handling for missing dates and other key safety data are described in Section 9. With respect to PK data, parameters will be derived as defined in [Section 7.8](#). Although these methods may employ some inherent estimation of missing values such as substitution of concentration values below the level of quantification for concentration summaries or calculation of the area under the time curve (AUC), no formal imputation methods will be performed for the study other than those specified in [Section 9.7](#).

6.4 INTERIM ANALYSIS AND DATA MONITORING

No formal interim analyses are planned to compare treatment arms with respect to efficacy or safety prior to formal completion of the trial.

6.5 MULTICENTER STUDIES

This study will be conducted at up to 3 study centers.

6.6 MULTIPLE COMPARISONS/MULTIPLICITY

No multiple comparison adjustments are planned for the safety and tolerability analyses, which are qualitative in nature. No multiple comparison adjustments will be employed for the PK or PD analyses, as the analyses of these endpoints focus more on estimation rather than inferential testing.

6.7 USE OF AN EFFICACY SUBSET OF PATIENTS

Not applicable.

6.8 ACTIVE-CONTROL STUDIES INTENDED TO SHOW EQUIVALENCE

Not applicable.

6.9 EXAMINATION OF SUBGROUPS

Subgroup analyses of 24-hour average ABPM assessments, trough pulse and BP assessments and treatment-emergent adverse events (TEAEs) will be performed by gender.

7. ANALYSIS METHODS

7.1 ANALYSIS POPULATIONS

The following analysis populations will be defined for the study:

Safety Population: The Safety Population will consist of all patients who received at least 1 dose of study drug and will be grouped according to actual study drug taken. All safety and tolerability assessments will be performed using the Safety Population.

PD Population: The PD Population will consist of all patients who received at least 1 dose of study drug and had at least 1 postdose PD assessment. All analyses of PD data will be performed using the PD Population.

PK Population: The PK Population will consist of all patients who received at least 1 dose of IW-1973 and had at least 1 postdose PK parameter assessment without events or deviations affecting the PK results. All analyses of PK data will be performed using the PK Population.

7.2 PROTOCOL DEVIATIONS

Protocol deviations will be listed by patient.

7.3 DISPOSITION OF PATIENTS

The number and percentage of patients who were included in each of the 3 analysis populations (Safety, PK, and PD), completed the study or discontinued early (along with the reasons for discontinuation) will be presented. A patient who has signed the ICF and has been randomized ceases participation in the study, regardless of circumstances, before completion of the Clinic Period will be considered to have discontinued early from the study. A patient will be considered to have completed the study after completing the Clinic Period and the End of Trial Visit.

In addition, data listings of patient disposition, including all patients who failed screening or terminated early, will be presented.

7.4 DEMOGRAPHIC AND BASELINE CHARACTERISTICS

Patient demographics (age, sex, race, ethnicity, weight, height, and body mass index [BMI, defined as weight in kg divided by height in meters squared]) and other baseline characteristics will be summarized for the Safety Population.

If either the PD or PK Population differs from the Safety Population, the presentation will be repeated for the respective populations.

7.5 MEASUREMENTS OF TREATMENT COMPLIANCE

This is an in-clinic dosing study and, therefore, no assessment of compliance is necessary. A data listing containing the study drug dosing information will be provided.

7.6 EXTENT OF EXPOSURE

This is an in-clinic dosing study and therefore no assessment of exposure is necessary, other than the data listing of study drug dosing information.

7.7 PHARMACODYNAMIC (PD) ANALYSIS

7.7.1 PD Parameters

The PD parameters are described below:

Ambulatory BP Monitoring

- Change from time-matched baseline in 24-hour average systolic BP, MAP, diastolic BP, and pulse. The 24-hour average for a postdose day is defined as the average of ambulatory assessments from the time of dosing on that day to the time of dosing on the next day. Time-matched baseline is defined as the average of ambulatory assessments from the time corresponding to dosing on Day -1 to the time of dosing on Day 1.
- Change from time-matched baseline in daytime (12-hour) average systolic BP, MAP, diastolic BP, and pulse. The daytime average on any postdose day is defined as the average of the 30-minute average ambulatory assessments from the time of dosing on that day to 12 hours postdose. Time-matched baseline is defined as the average of ambulatory assessments from the time corresponding to dosing on Day -1 to the time corresponding to 12 hours postdose.

- Change from time-matched baseline in nighttime average systolic BP, MAP, diastolic BP, and pulse. The nighttime average on any postdose day is defined as the average of the 30-minute ambulatory assessments from 12 hours postdose on that day to 1 hour before the time of dosing on the next day. Time-matched baseline is defined as the average of ambulatory assessments from the time corresponding to 12 hours postdose on Day -1 to 1 hour before the time of dosing on Day 1.
- Change from time-matched baseline in 4-hour averages of systolic BP, MAP, diastolic BP, and pulse. The 4-hour averages are calculated from the time of dosing on the ABPM assessment day, using the 30-minute average values. Baseline is defined as the corresponding 4-hour average on Day -1.
- Change from time-matched baseline in systolic BP, diastolic BP, MAP, and pulse at 30-minute postdose intervals. See Section 9.8 for details on calculation of assessment time intervals. Baseline is defined as the corresponding 30-minute average on Day -1.

Supine Pulse and BP Measurements

- Change from trough baseline in trough supine systolic BP, diastolic BP, and pulse. Postdose trough values are defined as the supine assessments performed 24 hours after the AM dosing. Trough baseline is defined as the Day 1 AM predose assessment.
- Change from study baseline in supine systolic BP, diastolic BP, and pulse.
- Proportion of patients meeting target postdose supine blood pressure levels of systolic BP < 130 mmHg and diastolic BP < 80 mmHg.

Endothelial Function and Exploratory Vascular Physiology Assessments

- Change from study baseline in RHI, AI and AI-75.

Metabolic Assessments

- Change from study baseline in insulin resistance (HOMA-IR). HOMA-IR will be calculated using the Homeostatic Model Assessment to estimate insulin resistance (HOMA-IR).(2,3)
The HOMA-IR equation is

$$HOMA-IR = \frac{(FSI \times FPG)}{22.5}$$

where FSI is the fasting serum insulin concentration (mU/l)

FPG is the fasting plasma glucose (mmol/l)

- Change from study baseline in metabolic assessments, fasting plasma glucose, serum insulin, hemoglobin A1C, cholesterol, HDL, LDL, triglycerides, weight, and BMI.

Platelet Function Assessments

- Change from study baseline in platelet function assessments [VerifyNow - P2Y₁₂ reaction units (PRU) and Aspirin]
- Proportion of patients with decreased platelet reactivity (VerifyNow) defined as <180 for PRU and <=549 for Aspirin
- Change from study baseline in the following platelet activation markers assessed in both platelet rich plasma (PRP) and whole blood samples (WB), and for different agonists (no agonist, ADP 0.5 μM [Low ADP], ADP 20 μM [High ADP], TRAP 1.5 μM [low TRAP], and TRAP 20 μM [High TRAP]):
 - % platelets positive for activated GPIIb-IIIa
 - % platelets positive for Surface P-Selectin
 - relative abundance of activated GPIIb-IIIa on platelet surface
 - relative abundance of P-Selectin on platelet surface
- Change from study baseline in platelet count

[REDACTED]

[REDACTED]

7.7.2 PD Analysis

Descriptive statistics will be presented for the observed and change from baseline results for the PD parameters at each scheduled timepoint by treatment group. Least squares means, standard errors and 95% confidence intervals for each treatment, as well as the least squares means, standard errors and 95% confidence intervals for each IW-1973 group minus placebo difference from an ANCOVA model with treatment as a fixed effect and baseline as a covariate will be presented for all the change-from-baseline endpoints, with the exception of [REDACTED] and VerifyNow assessments.

Subject incidence and percentages will be presented for the proportion of patients that meet target BP criteria. Percentages will be calculated based on the total number of PD subjects.

Shifts from baseline to each later timepoint will be tabulated for patients with decreased platelet reactivity.

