- AUC_{tau} : Area under the plasma concentration time curve during a dosing interval (τ)
- AUC_{inf} : Area under the plasma concentration time curve extrapolated to infinity
- C_{max} : Maximum observed plasma concentration, occurring at T_{max}
- C_{trough} : Trough plasma concentration observed at the end of a dosing interval (collected before the next administration)
- CL/F : Apparent total body clearance after oral administration
- $t_{1/2}$: Apparent terminal phase half-life
- T_{max} : Time of maximum observed plasma concentration
- V_z/F : Apparent volume of distribution during the terminal phase after oral administration

Safety

Physical examination, vital sign parameters, 12-lead electrocardiograms (ECGs), clinical laboratory evaluations (including clinical chemistry, hematology, coagulation, urinalysis), and patient- and Investigator-reported AEs will be evaluated. Estimated glomerular filtration rate (eGFR) by the Chronic Kidney Disease Epidemiology Collaboration (CKD-EPI) creatinine equation and urine albumin creatinine ratio (UACR; urine albumin [mg/dL] / urine creatinine [g/dL]) will be calculated.

Statistical Methods:

Sample Size Determination

Sample size for this trial was determined outside statistical considerations.

Analysis Populations:

All patients who receive at least 1 dose of study drug will be included in the Safety Population.

All patients who receive at least 1 dose of study drug and have at least 1 postdose PK parameter assessment will be included in the PK Population.

All patients who receive at least 1 dose of study drug and have at least 1 postdose PD assessment will be included in the PD Population.

Statistical Analysis

Descriptive statistics (n, mean, standard deviation, minimum, median, interquartile range, and maximum) will be calculated to summarize continuous variables. Frequency and percent of patients in each category will be calculated to summarize categorical variables.

Pharmacodynamic Analyses

Summary statistics will be provided by treatment for supine and ambulatory BP and pulse rate values, endothelial function testing (RHI value), platelet function assessment results, and HOMA-IR values; changes from baseline in these variables will be compared across treatment groups. Summary statistics will be provided by treatment for the proportion with postdose supine BP less than 130/80 mm Hg.

Pharmacokinetic Analyses

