1. INTRODUCTION

1.1 BACKGROUND AND STUDY RATIONALE

The NO-sGC-cGMP (nitric oxide – soluble guanylate cyclase – cyclic guanosine 3',5'-monophosphate) pathway plays a critical role in the cardiovascular system. In the vascular endothelium, sGC is stimulated by NO to produce cGMP, which acts on downstream targets including cGMP-dependent protein kinases, phosphodiesterases, and ion channels. This leads to relaxation of the vascular smooth muscle and vasodilation. In addition, intracellular cGMP is involved in processes that affect vascular proliferation, fibrosis, and inflammation. Impaired NO-sGC-cGMP signaling, has been implicated in the pathogenesis of cardiovascular diseases such as systemic and pulmonary hypertension, coronary artery disease, congestive heart failure, peripheral vascular disease, atherosclerosis, and kidney disease. Agents that stimulate sGC to increase cGMP production (1,2) may be useful for treating and/or preventing a broad range of diseases that may ensue from dysfunction in the fundamental NO-sGC-cGMP pathway.(3,4)

This exploratory, proof-of-concept study will evaluate the safety, tolerability, PK, and PD of 2 dosing regimens of daily 40 mg IW-1973 administered orally for 2 weeks to patients with type 2 diabetes mellitus and hypertension. This study is designed to explore the tolerability profile of the MAD MTD, 40 mg IW-1973, in a patient population, and to explore whether tolerability can be improved with an initial week of BID dosing.

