2. STUDY OBJECTIVES

To compare the safety, tolerability, PK profile, and PD effects of 2 treatment regimens of IW-1973 Tablet (40 mg per day) administered orally for 2 weeks to patients with stable type 2 diabetes mellitus and hypertension.

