3.2 DISCUSSION OF STUDY DESIGN INCLUDING THE CHOICE OF CONTROL GROUPS

A double-blind, placebo-controlled, randomized study design was chosen to investigate the safety PK, PD, and tolerability of 2 daily 40-mg IW-1973 dosing regimens. Patients will be randomized to ensure that the treatment groups are comparable and to minimize the potential for selection bias. The study will be double blind and treatments will be masked to ensure that the subjects and clinic staff are unaware of the dosing assignment and to minimize potential for bias in study assessments or in reporting of AEs. Placebo was chosen as the control so that the rate of spontaneously occurring AEs can be determined and to reduce the potential for bias in the reporting of AEs. Randomization will occur so that, within a particular cohort, an optimal number of subjects can be exposed to a particular dose of IW-1973, while at the same time ensuring that a reasonable number of subjects across the cohorts receive placebo for AE and PD comparisons. This design is in accordance with the concepts in International Conference on Harmonisation (ICH) E10, Choice of Control Groups and Related Issues in Clinical Trials (International Conference on Harmonisation of Technical Requirements for Registration of Pharmaceuticals for Human Use, 2001).

Patients will be confined to the Study Center for the full duration of dosing through 24 hours after the final dose to allow monitoring of safety parameters and assessment of any PD effects of IW-1973. In addition, Stopping Criteria (Section [3.6](#)) have been established to ensure that dosing will stop should a safety signal be detected. Patients will have a Follow-up Visit 7 (\pm 2) days after the final dose of study drug and an End of Trial Visit 28 (\pm 3) days after the final dose to determine if any AEs have developed and if any AEs that were ongoing at the time of Discharge have resolved.

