2. STUDY OBJECTIVES

The objectives of the study are to compare the safety, tolerability, PK profile, and PD effects of 2 treatment regimens of IW-1973 Tablet (40 mg per day) administered orally for 2 weeks to patients with stable type 2 diabetes mellitus and hypertension.

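### The objective is to compare the two IW-1973 regimens, but the visible SAP text specifies no BID/QD versus QD/QD estimate or interval; its only between-group estimates are active minus placebo for PD.

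*SAP*

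**What the plan says.** **Objective.** Protocol section 2 reads "To compare the safety, tolerability, PK profile, and PD effects of 2 treatment regimens of IW-1973 Tablet (40 mg per day", and SAP section 2 repeats it. Protocol section 1.1 gives the specific question: "to explore whether tolerability can be improved with an initial week of BID dosing".

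**Placebo.** Protocol section 3.2 explains the control arm as "ensuring that a reasonable number of subjects across the cohorts receive placebo for AE and PD comparisons".

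**PD.** The protocol synopsis says that "changes from baseline in these variables will be compared across treatment groups", without naming a contrast. SAP 7.7.2 gives least squares means, standard errors and intervals for each arm, and "95% confidence intervals for each IW-1973 group minus placebo difference from an ANCOVA model". It specifies no active-versus-active difference.

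**PK.** SAP 7.8.2 summarizes parameters by arm, and SAP 6.1 adds the geometric mean and CV. The ratios in SAP Table 3 (RAUCtau, RCmax, RCtrough, SCmax) compare days within a patient, not regimens.

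**Tolerability.** Protocol 3.9.3.4.1 plans a summary of first-week events by arm. SAP 7.9.1 presents TEAEs by arm for Week 1 and Week 2, and hypotension events by arm only.

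**Stance.** SAP 6.6 says of PK and PD that "the analyses of these endpoints focus more on estimation rather than inferential testing", and describes "the safety and tolerability analyses, which are qualitative in nature". SAP 6.1 and Protocol 3.9.3.1 make any inferential statistic descriptive. SAP section 8, which lists additions and changes to the planned analyses, adds no regimen contrast.

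**The concern.** The question whether splitting the dose in Week 1 helps is a BID/QD versus QD/QD question. Active-minus-placebo differences answer something else: what each regimen does relative to no drug. A plan that emphasizes estimation, and already fits a model containing all three arms, would be expected to report the contrast its objective names.

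Without it, readers are left to compare two arm summaries, or two placebo differences that share the same six placebo patients. Neither gives a direct interval for the regimen difference. The choice of endpoints and days for that comparison also stays open until the data have been seen.

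**Working it through.** **1. Arm sizes.** 26 patients at 5:5:3 (Protocol 3.9.1): 26 × 5/13 = 10, 26 × 5/13 = 10, 26 × 3/13 = 6. This is two full blocks of 13 (SAP 3.3). SAP section 4 gives no SD, effect size or target precision, so there is no stated precision figure to reproduce.

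**2. PD contrast.** The ANCOVA has three treatment levels and one covariate, so the residual df with complete data are 26 − 4 = 22, and t(0.975, 22) = 2.074. The half-width is t × SD × √(1/n₁ + 1/n₂), before any loss from chance baseline imbalance.
- BID/QD minus QD/QD: 2.074 × √(1/10 + 1/10) = 0.93 SD.
- Either active arm minus placebo: 2.074 × √(1/10 + 1/6) = 1.07 SD.
- The unspecified contrast is about 13% narrower than the planned ones (0.927/1.071 = 0.866).

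The documents give no residual SD. For an assumed 8 to 12 mmHg, the half-widths are 7.4 to 11.1 mmHg for the regimen contrast and 8.6 to 12.9 mmHg for a placebo contrast.

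**3. Why arm intervals do not replace it.** One active-arm mean has a half-width of 2.074 × √(1/10) = 0.656 SD. Two such intervals stop overlapping only at a gap of 2 × 0.656 = 1.31 SD, whereas the direct interval excludes zero beyond 0.93 SD. The exact SE of the difference also does not follow from the two arm SEs, because adjusted means are correlated through the covariate.

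**4. RHI.** Protocol 3.7.4.2 measures it only where EndoPAT is available. Assumed arms of 7/7/4: df = 14, t = 2.145, half-width 2.145 × √(2/7) = 1.15 SD. Assumed 5/5/3: df = 9, t = 2.262, half-width 2.262 × √(2/5) = 1.43 SD.

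**5. Tolerability (illustrative counts, Newcombe 95% interval).**
- Week 1 TEAEs 3/10 on BID/QD v 6/10 on QD/QD: −30 points, −60 to +12.
- Week 1 hypotension events 1/10 v 4/10: −30 points, −60 to +8.
- Over all 11 × 11 = 121 possible results, the half-width runs from 20 to 37 points.

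**6. PK ratio.** With 10 v 10 on the log scale, df = 18 and t = 2.101. The 95% factor is exp(2.101 × √ln(1 + CV²) × √0.2). For an assumed between-patient CV of 20%, 30% or 40%, the interval is the ratio multiplied and divided by 1.20, 1.32 or 1.44.

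**7. Number of added PD contrasts.** A 24-hour record has 24/4 = 6 four-hour averages, taking them as consecutive from dosing. With the 24-hour, daytime and nighttime averages that is 9 summaries × 4 parameters = 36 per day.
- Week 1: 36 × 2 days + 3 trough + 1 HOMA-IR = 76.
- Week 2: 36 + 3 trough + 1 HOMA-IR + 1 RHI = 41.
- The 30-minute intervals would add 47 × 4 × 3 = 564.

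If the regimens do not differ, about 76/20 ≈ 4 and 41/20 ≈ 2 of these intervals would exclude zero by chance. The endpoints are correlated, so such exclusions would tend to cluster.

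**The case against.** **The study is exploratory, and comparing does not require an interval.** This is fair, and it rules out calling the omission an error. But the SAP already commits to model-based differences with intervals against placebo, so the same descriptive treatment of the objective's own contrast is in keeping with it.

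**Tolerability is handled in the declared way.** This stands. Week 1 events are tabulated by arm, and the SAP calls the safety analysis qualitative. With 10 v 10 an interval is blunt: starting from 1 to 4 events in the lower arm, the other arm needs five more before the Newcombe interval excludes zero. What the interval adds is protection against over-reading a gap such as 3/10 v 6/10.

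**Readers can do the subtraction.** Partly true. The PD point difference and the PK ratio of geometric means follow from reported values. SAP 6.1 also limits Day 1 PK summaries to the two active arms, and SAP 7.8.3 plots individual values by arm. The exact PD interval does not follow.

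**The placebo contrast has its own purpose.** Agreed; Protocol 1.1 and 3.2 support it. The proposal adds to it and replaces nothing.

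**The contrast may be specified elsewhere.** SAP section 1 puts table specifications in a separate document, and part of SAP 7.7.2 is redacted. The point therefore concerns the visible text only.

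**Conclusion.** The visible SAP text does not commit to an estimate or interval for the comparison that both documents state as the objective. The remedy is a worthwhile, inexpensive addition: no data are lost, and by-arm results already permit an informal comparison.

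A reader might infer more: that the trial cannot meet its objective, that it is underpowered, that type I error is uncontrolled, or that the synopsis commitment has been broken. The documents do not support these readings. No power claim or confirmatory test is made, inference is descriptive throughout, and the synopsis sentence names no contrast that the SAP has dropped. Nor can it be said that the sponsor has no such analysis, since the table specifications are not available.

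The size is one of precision: a half-width of about 0.93 residual SD for PD and 20 to 37 points for incidence. These figures rest on full arms of 10, 10 and 6 and complete data. The mmHg and PK figures also rest on the assumed SDs and CVs, and the RHI figures on assumed arm sizes. The event counts are illustrative.

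**What to change.** Make three additions, all labelled descriptive under SAP 6.1, before unblinding.

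1. **SAP 7.7.2.** Add the BID/QD minus QD/QD least squares mean difference, SE and 95% interval from the same ANCOVA.
   - Lead with Week 1: Day 1 and Day 7 ABPM 24-hour, daytime, nighttime and 4-hour averages; Day 8 trough supine BP and pulse; Day 8 HOMA-IR.
   - Give Week 2 as secondary, because both arms take the same dose from Day 8: Day 13 RHI with n per arm; Day 14 ABPM; Day 15 trough and HOMA-IR.
   - Leave out the 30-minute intervals.
2. **SAP 7.8.2.** Add the BID/QD to QD/QD geometric mean ratio with a 95% interval for Day 1 AUC24 v QD AUCtau, Day 1 Cmax,24 v QD Cmax, and Day 7 Cmax. Note that Table 3 defines Day 7 Cmax relative to the morning dose, so it compares peaks after different tablet doses. Give Day 14 AUCtau and Cmax as secondary.
3. **SAP 7.9.1.** Add the BID/QD minus QD/QD difference in Week 1 TEAE incidence, and in Week 1 Appendix 1 hypotension events, each with a Newcombe 95% interval.

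State with the results that the intervals are wide and unadjusted, and that about 1 in 20 would exclude no difference by chance if the regimens do not differ. If the table specifications already hold these contrasts, state them in the SAP text.

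**Cost.** SAP wording, extra contrasts from models already planned, five PK ratios, two risk differences and one new by-week hypotension table. The Day 1 BID inputs (AUC24 and Cmax,24) are already in Table 3. No new data or patients are needed.
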